6.9. Medication errors and overdose

Medication errors in this study may arise when the drug is administered at the wrong time or when the wrong dose strength is taken. Patient medication errors should be recorded in the relevant section in the CRF. In the event of an error in the administration of the medication, the Sponsor should be informed immediately.

Medication errors must be reported irrespective of the presence of an associated AE/SAE, including:

- Medication errors involving patient exposure to the IMP.
- Any possible medication errors or use of the medication not defined in the protocol which implicate the participating patient or not.

Regardless of whether the medication error is accompanied by an AE or not, in the judgment of the investigator, the medication error should be recorded in the AE page.

6.10. ***Treatment compliance***

Patients will receive treatment under the supervision of a physician licensed in the administration of radioisotopes. Personnel will check the administration volume and total radioactivity injected. The activity/dose (total and per body kilogram) will be recorded in the source data and the appropriate CRF.

6.11. ***Dose adjustments***

Every effort will be made to administer the full dosing regimen of radium-223. Adjustment of dose level is not permitted. Study visits during the treatment period should occur at four weeks intervals (within a window \pm 7 working days).

Dosing delays may be instituted under the following situations:

- Disease progression:

In this patient population, disease progression is expected. Bone pain is a prominent symptom; other symptoms may include fatigue, nausea, anorexia, depression, constipation (also secondary to opioids), bowel and bladder symptoms, lymphedema, neurological, and hematological complication as well as metastases to other organs, such as liver and lung. The investigator should delay cytotoxic chemotherapy, other systemic radioisotope, radiotherapy, or other investigational drug until the follow-up period. If such treatments have to be given during the treatment period, further study drug administrations must be discontinued. Patients with disease progression may continue treatment at the Investigator's discretion.

- Myelosuppression:

Treatment-related changes in hematology parameters may occur:

- If a patient experiences grade 3 or 4 neutropenia, thrombocytopenia, or anemia lasting \leq 14 days, the administration of study drug should be delayed until recovery to grade 2 or better. A delay of up to 4 weeks is permitted.
- If a patient experiences grade 3 or 4 neutropenia, thrombocytopenia, or anemia lasting $>$ 14 days, further study drug administrations must be discontinued.
- Blood transfusion is acceptable between study drug administrations. Use of biologic response modifiers, such as G-CSF or GM-CSF, is allowed in the management of acute toxicity.

- Gastrointestinal events:

- Diarrhea. Diarrhea should be treated as per local practice. A further dose of study medication should not be given before diarrhea is recovered to no higher than CTCAE grade 2.
- Nausea/Vomiting. Nausea or vomiting should be treated as per local practice. A further dose of study medication should not be given before nausea or vomiting is recovered to no higher than CTCAE grade 2.

- Surgical intervention:

If surgery is required, the patient should continue with study treatment, if this is considered safe in the treating investigator's opinion. The surgeon needs to be notified that the patient has been given radioactive drug, and needs to follow the guidelines for radioactive protection.

- Non-pathological fractures:

For traumatic fractures in weight-bearing bones during treatment phase, the study drug administration should be delayed for two to four weeks from the time of fracture.

- Any other toxicity:

Local practice will apply. A dose delay of more than four weeks (maximum eight weeks between two injections) will lead to study drug discontinuation.

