Study Treatment:	
Once the informed consent has been signed and the study screening criteria have been confirmed, the patient will be treated with radium-223 at a dose of 55 kBq (after 2015 NIST implementation) per kilogram body weight, given at four-week intervals for six intravenous injections. Adjustment of dose level is not permitted.
 
Patients will receive study treatment according to the protocol and will be prematurely discontinued in the following situations: disease progression, occurrence of unacceptable side effects, death, or withdrawal of consent, whichever occurs first.
 
Patients who complete the study treatment during its active treatment phase will enter a follow-up period, with radiological tumor assessment every three months (± 7 working days) until disease progression and safety evaluation to follow-up of symptomatic skeletal related events until reach 2 years from the last dose of study treatment. If patient discontinued treatment for any reason other than progression, tumor reevaluation will be included in the assessment. After disease progression, a safety follow-up visit will be performed within three following months (including survival status and post-study anticancer therapy evaluation) and 2 years after last dose of study drug. Safety evaluation after progression will include follow-up of symptomatic skeletal related events and overall survival.

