3.2. Study schedule

The design of this study is divided into three well-defined phases:

- **Screening phase**

During this phase, subject eligibility is determined, including the documentation of baseline characteristics. This phase of the study will begin once the informed consent is signed by the patient and the procedures to be performed are described in section 5.1 of the protocol.

- **Treatment phase:**

When a patient is identified and all the study screening criteria have been met, a baseline blood sample will be collected to perform CTCs the patient will be treated with radium-223 at a dose of 55 kBq (after 2015 NIST implementation) per kilogram body weight, given at four-week intervals for six intravenous (IV) injections.

Patients will receive study treatment according to the protocol and will be prematurely discontinued if one of the following situations arises:

- Disease progression is confirmed radiologically and unequivocally. An event for progression will be determined by The Prostate Cancer Clinical Trials Working Group (PCWG2) modified criteria defined as the time from inclusion to the first event in clinical, radiological, or biochemical progression, or death as[21]:

- Bone metastases: The appearance of \geq two new lesions, and, for the first reassessment only, a confirmatory scan performed six or more weeks later that shows a minimum of two or more additional new lesions. The date of progression is the date of the first scan showing the changes.

- Soft-tissue lesions: Assesed according to the Response Evaluation Criteria in Solid Tumors (RECIST criteria) version 1.1.[22].

- Symptoms: Consider independently of other outcome measures. Document pain/analgesia at entry and measure repeatedly at three- to four-week intervals. Ignore early changes (\leq 12 weeks) in pain or health-related quality of life (HRQOL) in the absence of compelling evidence of disease progression. Confirm progression of pain or HRQOL endpoints \geq three weeks later.

- Clinical deterioration: Consider independently of other outcome measures. A deteriorating patient is one who moves from one clinical state to a worse clinical state which increases their individual risk of morbidity, including organ dysfunction, protracted hospital stay, disability, or death.[23].

- AEs which, according to the protocol or in the opinion of the investigator, can cause serious or permanent damage or which rule out further treatment with the study drug.

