- Major study protocol non-compliance.
- Patient's withdrawal from the study.

-
- Dead.
 - Study is canceled by the Sponsor.

Patients may continue receiving commercial radium-223 (Xofigo®), if it is found to offer clinical benefits in the opinion of the investigator.

• **Follow-up phase:**

Once the treatment phase is completed, patients will enter a follow-up period with radiological tumor assessment every three months (± 7 working days) until disease progression and safety evaluation during 2 years from the last dose of study treatment. If patient discontinued treatment for any reason other than progression, tumor reevaluation will be included in the assessment. After disease progression, a safety follow-up visit will be performed within three following months and 2 years after the last dose of study treatment (including survival status and post-study anticancer therapy evaluation). Safety evaluation after progression will include follow-up of symptomatic skeletal related events and overall survival.

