5.5. Discontinuation of patient, study, or site participation

Treatment discontinuation: Patients have the right to withdraw from the study at any time and for any reason, without being required to state their reasons for doing so. The investigator has the right to discontinue a patient from study treatment or from the study for any medical condition that the investigator determines may jeopardize the patient's safety if he continues in the study, for reasons of non-compliance (e.g., missed doses, visits), or if the investigator determines it is in the best interest of the patient.

Patients should also be withdrawn from the study treatment if they experience disease progression as defined by the RECIST criteria version 1.1. Further details regarding study discontinuation due to side effects are described in section 6.11.

Patients who withdraw from study treatment prematurely will be followed up in accordance to section 5.3 except for those patients who withdraw their consent and who do not wish to undergo a follow-up. The main reason for discontinuation should be recorded in the appropriate section in the CRF.

Study discontinuation:

Patients will be withdrawn from the study (e.g., from any subsequent study procedure) for any of the following reasons:

- Withdrawal of consent.
- Lost to follow-up.

If patient is lost to follow-up, site personnel must do their utmost to re-establish contact with the patient and determine the reason for their withdrawal. All measures taken to undertake follow-up should be recorded.

When a patient withdraws before the end of the study, the reason for withdrawal should be recorded in the CRF and in the original document. Patients who withdraw from the study will not be replaced.

In addition, the Sponsor reserves the right to terminate this study at any time. Reasons for terminating the study may include, but are not limited to, the following:

- The incidence or seriousness of AEs in this or other studies indicates a potential health risk to patients.
- Patient enrollment is unsatisfactory.
- Data recording is inaccurate or incomplete.

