6.2. Drug supply

The latest version of study document Summary of Product Characteristics (SmPC) for radium-223 (Xofigo[®]) includes updated information on this drug.

The Sponsor will provide radium-223, which will be manufactured by the contract manufacturer: Institute for Energy Technology, Isotope laboratories, Kjeller, Norway. The products will be produced according to Good Manufacturing Practice (GMP), and will be delivered in a glass vial,

ready-to-use, with a certified activity. Radium-223 will be shipped in a lead container and type A radioactive package according to international transportation guidelines for radioactive materials. The alpha-pharmaceutical radium-223 is a ready-to-use, sterile, non-pyrogenic, clear, and color less aqueous solution of $^{223}\text{RaCl}_2$ for IV administration. The product is isotonic and has a pH of 6.0-8.0 with a pre-calibration of 14 days.

Single-use vials contain 6 mL solution at concentration of 1100 kBq/mL (27 microcurie/mL) at the reference date with a total radioactivity of 6.6 MBq the reference date (after 2015 NIST implementation). When administered on a day other than the reference day, the volume should be corrected according to the physical decay table.

Radium-223 has a shelf life of 28 days from production day, when stored at ambient temperature. The shelf life has been demonstrated for temperatures from cold storage (2-8°C) up to 40°C. In addition, it has been shown that the product quality is not jeopardized upon freezing. All study drugs will be labeled according to the requirements of local law and legislation. Label text will be approved according to the Sponsor's agreed procedures.

For all study drugs, a system of numbering in accordance with all requirements of GMP will be used, ensuring that each dose of study drug can be traced back to the respective bulkware of the ingredients. Lists linking all numbering levels will be maintained by the Sponsor. A complete record of batch number and expiry dates for all study treatments as well as the labels will be maintained in the Sponsor study file.

Once the study has ended, patients may continue receiving commercial radium-223, if it is found to offer clinical benefits in the opinion of the investigator

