7.2. Reporting of AEs

AEs will be collected starting from the first procedure required by the study up to three months after patient's disease progression. Safety evaluation after progression will include follow-up of symptomatic skeletal related events until reach 2 years from the last dose of study treatment.

All study patients who experience AEs will be closely monitored during this time. All AEs should be recorded in the CRF.

All signs, symptoms, and results of procedures with abnormal diagnoses that are clearly related should be grouped together and reported as a single diagnosis or disorder wherever possible. Any other event that does not fulfill this definition will also be reported separately.

Reporting of SAEs and reporting period

Reporting requirements will comply with all applicable local regulations regarding safety reporting.

All SAEs and AESIs defined in the protocol will be reported to the Sponsor within a period of 24 hours from the time the investigator or any other member of the site staff becomes aware of the event, as follows:

- Regardless of the study drug received by the patient and whether or not the investigator considers this event to be related or not to the study drug, all SAEs and AESIs (as defined in this protocol), will be reported to MedSIR immediately, no later than 24 hours after any member of the study site staff becomes aware of the event.
- All information regarding the SAE and AESI should be obtained and recorded in full using the SAE form and sent to MedSIR.
- Follow-up information, copies of test results, event outcome and the opinion of the investigator as to the relationship between the IMP and the SAE and AESI, accompanied by other applicable documentation when it is requested, will be sent along with the SAE form, if available on the day the event is reported or as soon as possible if it is not.
- The original SAE reporting form of the Sponsor should be kept on file with the documentation from the CRF at the study site(s).

All SAE forms will be sent by the investigator or investigator staff to the Sponsor by e-mail and fax as indicated below:

E-mail: [contact]

Fax: [name]

Follow-up of the SAEs and AESIs will continue until they resolve, a stable outcome is reached, patient is lost to follow-up, or the patient dies.

MedSIR will be responsible for ensuring that events are reported to the European Medicine Agency (EMA), competent authorities, within the stipulated period, as needed.

AESIs

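### Section 6.11 lets radium-223 continue after progression while the synopsis, 3.2, 3.5, 5.5 and SAP 4.5 stop it; the progression triggers and adverse event windows also disagree

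*Protocol*

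**What the plan says.** Protocol section 6.11 (Dose adjustments) lists disease progression among the situations in which an injection may be delayed. It closes that item with: "Patients with disease progression may continue treatment at the Investigator's discretion". It sets no limit by type of progression or by number of further injections.

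Five other places point the other way:

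- **Protocol synopsis, Study Treatment, and SAP 4.5** (same wording): patients "will be prematurely discontinued in the following situations: disease progression, occurrence of unacceptable side effects, death, or withdrawal of consent, whichever occurs first".
- **Protocol 3.2:** patients "will be prematurely discontinued if one of the following situations arises", and the first situation is "Disease progression is confirmed radiologically and unequivocally". A modified PCWG2 list follows, covering bone, soft tissue, symptoms and clinical deterioration.
- **Protocol 3.5:** refers back to the 3.2 reasons for interrupting treatment.
- **Protocol 5.5:** "Patients should also be withdrawn from the study treatment if they experience disease progression as defined by the RECIST criteria version 1.1".

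On commercial drug, 3.2 says directly after its list of stopping reasons: "Patients may continue receiving commercial radium-223", with investigator-judged benefit as the condition and no timing. Section 6.2 says: "Once the study has ended, patients may continue receiving commercial radium-223, if it is found to offer clinical benefits in the opinion of the investigator".

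On adverse events, 7.2 says: "AEs will be collected starting from the first procedure required by the study up to three months after patient's disease progression". Appendix 1 note 7 runs recording to the treatment discontinuation visit, which it also labels the end of study visit. SAP 8.4.3 assesses deaths and serious events up to three months after study discontinuation, and non-fatal events to the same point or to the start of new anticancer treatment if that is earlier.

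**The concern.** A site whose patient has progressed needs one instruction about the next injection. The protocol gives at least two, and the passages that stop treatment do not agree on what counts as progression. Whichever section the site follows, it can claim compliance.

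The number of injections and the end-of-treatment date then depend partly on which page was read. Toxicity counts, time to first symptomatic skeletal event and overall survival can all be affected by injections given after progression. So can the biomarker sampling. Under Appendix 1 note 11, a patient who stops because of progression gives one sample at that point, while a patient who continues gives a progression sample and a later end-of-treatment sample. The comparison of AR-V7 and CTCs between start and end of study would mix the two.

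Section 7.2 adds a second difficulty. Its adverse event window is tied to progression and not to the last injection, which fits a trial where dosing stops at progression but not one where it may go on.

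**Working it through.** The plan states no figure on this point. The check is a comparison of text followed by calendar arithmetic.

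**1. Same patient, each passage.**

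| Passage | Trigger | Instruction on study drug |
|---|---|---|
| Synopsis; SAP 4.5 | Disease progression, not qualified | Discontinue |
| 3.2 | Confirmed radiological progression, then a PCWG2 list that includes symptoms and clinical deterioration | Discontinue |
| 3.5 | Any reason in 3.2 | Interrupt |
| 5.5 | RECIST 1.1 progression | Should be withdrawn |
| 6.11 | Disease progression, not qualified | Delay is possible; may continue if the investigator so decides |

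Section 5.2 uses RECIST 1.1 for soft tissue and PCWG2 for bone. A patient with confirmed new bone lesions alone therefore meets the synopsis, 3.2 and SAP 4.5 triggers, is not clearly covered by 5.5, and may continue under 6.11. Eligibility requires bone metastases and no visceral metastases, so this is not an exotic case.

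**2. Can the passages be read together?** One could confine 6.11 to unconfirmed or purely symptomatic progression. The section does not say so, and its description of progression includes spread to organs such as liver and lung as well as symptoms. No other section cites 6.11 as an exception to the stopping rule.

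**3. Adverse event window under 7.2.** Inputs: six injections four weeks apart (6.1); first scheduled tumor assessment at the end of cycle 3, week 12 (5.2); at most eight weeks between two injections (6.11). Assumption: three months = 13 weeks (range 12 to 13.1).

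- On-time injections fall at weeks 0, 4, 8, 12, 16 and 20.
- Window end = progression week + 13. For week-12 progression: 12 + 13 = week 25 (range 24 to 25.1). Injection 6 at week 20 is inside.
- For on-time injection 6 to fall outside, progression must be dated before 20 − 13 = week 7 (range 6.9 to 8). That needs an unscheduled scan or an early clinical event.
- For week-12 progression, accumulated delay must exceed 25 − 20 = 5 weeks (range 4 to 5.1). If the first four injections were on time, a single maximum delay of 4 weeks puts injection 6 at week 24, which is not outside. Two maximum gaps (weeks 12, 20, 28) put it 28 − 25 = 3 weeks outside.
- With every gap at the maximum (weeks 0, 8, 16, 24, 32, 40), the injections at weeks 32 and 40 fall outside for week-12 progression. For week-24 progression the window ends at 24 + 13 = week 37, and only the week-40 injection falls outside.

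**4. Which injections are in dispute under 3.2.** Bone progression at the first reassessment needs a confirmatory scan six or more weeks later: 12 + 6 = week 18. Injections 4 (week 12) and 5 (week 16) have then been given on schedule, so only injection 6 remains in dispute. Soft-tissue progression needs no confirmatory scan (5.2), so it can put more injections in dispute.

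**The case against.** The strongest reply is that safety data would still be captured. Section 5.2 requires adverse event assessment on day 1 of every cycle and before each new dose, with monitoring through treatment and follow-up. Appendix 1 schedules adverse event reporting at every cycle. Section 7.1 requires the sponsor to be notified of possibly related serious events at any time after treatment ends. SAP 8.4.3 does not use progression as its clock. This stands: only 7.2 ties collection to progression. A reader might infer that toxicity after progression goes uncollected, or that patients are routinely injected after collection closes. The documents support neither. They support a disagreement between windows, with a gap under 7.2 alone in the limited cases above.

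Other stronger readings also fail:

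- **Number affected.** With exponential PFS and the plan's medians of 6.3 and 3 months, 1 − 2^(−t/m) at t = 12 weeks (2.76 months) gives 26% and 47%, or about 14 and 25 of 52 patients. A reader might take these as patients facing three disputed injections. They count progression, not dosing after it, and they ignore confirmation of bone lesions. Progression between weeks 12 and 20 would normally be seen at the week-24 scan, after an on-time sixth injection.
- **Exclusive wording.** A reader might infer that 5.5 stops treatment for RECIST progression alone, or that 6.2 confines commercial drug to the period after the study. Neither section says *only*, and 5.5 says *also*. The difference between 3.2 and 6.2 is unclear timing, not a proven contradiction.
- **Primary endpoint.** PFS is dated at progression (Protocol 8.3.1, SAP 7.1.1), so later dosing does not move it. A reader might look to the SAP 6.1 deviation for subjects not withdrawn per protocol, since its table footnote removes major deviations from the full analysis set. That entry concerns data obtained after withdrawal, and nothing ties it to dosing under 6.11.

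None of this touches the stop-or-continue contradiction.

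**Conclusion.** The contradiction is established from the text and depends on no numerical assumption: 6.11 permits what the synopsis, 3.2, 3.5, 5.5 and SAP 4.5 end, and the stopping passages use three different triggers. It should be corrected because it governs whether an injection is given. It bears on exposure, safety, the end-of-treatment sample, time to first symptomatic skeletal event and overall survival, and leaves primary PFS untouched. The documents do not allow an estimate of how many patients would be dosed after progression.

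The adverse event windows are a secondary inconsistency. Taking three months as 13 weeks, an injection falls after the 7.2 window only with progression dated before about week 7, or with more than about 5 weeks of accumulated delay after week-12 progression.

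**What to change.** - Reconcile the synopsis, 3.2, 3.5, 5.5, 6.11 and SAP 4.5 to one statement on study drug after progression, using one definition of progression. Which rule applies is for the sponsor to decide.
- Clarify between 3.2 and 6.2 when commercial radium-223 may be given.
- Align 7.2, Appendix 1 note 7 and SAP 8.4.3 to one adverse event window. If study dosing after progression remains possible, run the window from the later of progression and the last study injection. If it does not, that extension is unnecessary.
- Add a table of injections given after the progression date. Administered doses are already recorded in the CRF (6.10), so it can be derived from the dosing and progression dates.

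The cost is a short protocol amendment with a matching SAP edit, one added table, and slightly longer adverse event collection for any patient dosed after progression. No extra patients are needed.
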